Our study design incorporates innovative methodological features, including studying if assessing drink size can reduce drinking by itself and if depression modifies e-SBI efficacy. This will provide preliminary information related to how and for whom the e-SBI works. We expect to disseminate our findings via publications in scientific journals and through networks of participating organizations as well as networks of the local county and state perinatal health professionals and substance abuse treatment professionals. Because it begins to build an evidence base for e-SBI efficacy for reducing prenatal alcohol use, our study is of significance for improved maternal and child health. Findings will also impact the larger literature on cost-effective strategies to reduce alcohol-related harm.

Specific aims of the study are to:

- Aim 1. Adapt a computerized SBI (e-SBI) for drinking during pregnancy for use with women of childbearing age.
- Aim 2. Conduct a small randomized trial of the e-SBI with an intervention group (e-SBI, n=100) and a control group (usual care, n=100) at two WIC program sites.
- Aim 3. Use drink size assessment to better measure drinking outcomes, and explore efficacy for the drink size assessment component of the e-SBI.
- Aim 4. Explore if depression modifies alcohol use outcomes for e-SBI. We expect that within the intervention and control group each, women reporting depression will reduce their drinking less than those without depression.

(484 words)

CITATIONS

b) What is the major research question to be addressed in this project?

The study examines efficacy of electronic screening and brief intervention for reducing alcohol consumption among women of childbearing age.

2. Study Procedures: All project types)

a) Describe all study procedures. Please note: The box below is for text only. If you would like to add tables, charts, etc., attach those files in the [Attachment](#) section.

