The proposed study seeks to reduce excessive alcohol consumption among non-pregnant women of child bearing age as a primary prevention approach to reduce prenatal alcohol use. It is expected to provide important information relevant to public health efforts to reduce Fetal Alcohol Spectrum Disorders and to improve the health of mothers and their infants. The study includes a specific focus on cost-effective methods for screening and brief intervention (e-SBI) and on factors that affect the efficacy of e-SBI. Thus, the proposed study will impact not only public health efforts to reduce drinking in women of childbearing age women, but the larger body of science on the prevention of alcohol-related harm.

Because procedures to adapt e-SBI for use with non-pregnant women involves the input of WIC staff and local experts in maternal and child health, the proposed study will increase networking and collective action among professionals invested in improving women's health. We have already connected with the bay area perinatal advocates and integrated their input into our study implementation and planned dissemination of findings.

Explain why study risks are reasonable in relation to the potential benefits to subjects and to society.

Importance of the knowledge to be gained

There is an urgent need for cost-effective tools for delivering SBI to meet challenges to increase health care access for the implementation of the Affordable Care Act (ACA) in a weak economy with dwindling health care resources. The proposed study will addresses barriers to recommended screening and brief intervention and to the prevention of drinking during pregnancy with a novel electronic SBI to reduce drinking in women before they become pregnant. It will also test if drink size assessment alone can reduce drinking, providing data on possible cost effective interventions. Thus, the proposed study is of significance for the prevention of Fetal Alcohol Spectrum Disorders and for improved maternal and child health. Scientific knowledge on what may reduce or enhance e-SBI efficacy will also impact public health prevention efforts beyond that for childbearing age women and help further refine cost-effective strategies to reduce alcohol-related harm.

8. Administrative Safeguards: (All project types)

a. Are administrative safeguards for data security being met or is there justification for not meeting specific safeguards or providing an alternative safeguard? Yes No

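### Aim 4 asks whether depression modifies e-SBI efficacy, but its only stated expectation is a depression gap within each arm, which does not answer that question

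*Protocol*

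**What the plan says.** The summary in Protocol section 1(a) says the study will examine "if depression modifies e-SBI efficacy" and that this will give "preliminary information related to how and for whom the e-SBI works". Aim 4, in the same section, is to "Explore if depression modifies alcohol use outcomes for e-SBI". The sentence that follows is the only one in the document that says what is expected of depression: "We expect that within the intervention and control group each, women reporting depression will reduce their drinking less than those without depression".

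Section 7 (Benefits) speaks in general terms of a focus "on factors that affect the efficacy of e-SBI" and of "Scientific knowledge on what may reduce or enhance e-SBI efficacy". It does not name depression, so the point rests on section 1(a) alone.

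Aim 2 gives the arm sizes: "intervention group (e-SBI, n=100) and a control group (usual care, n=100". The protocol states no depression prevalence, outcome SD, significance level or power.

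**The concern.** In a two-arm trial, efficacy is the difference between e-SBI and control. Asking whether depression modifies it means asking whether that difference is the same in women with and without depression. The stated expectation compares depressed with non-depressed women inside each arm separately, and never compares the arms. It is a statement about prognosis.

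If it is confirmed, the trial will have shown that depression predicts a smaller reduction in drinking. It will not have shown that depression weakens or strengthens the e-SBI. The risk is that a gap seen in both arms is reported as evidence on whom the e-SBI works for. A related risk is that a gap significant in one arm but not in the other is read as modification.

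**Working it through.** The protocol gives no figure to reproduce, so the check is algebraic, with illustrative numbers.

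**Definitions.** Let I and C be the mean reduction in drinking under e-SBI and control, with subscript 0 for non-depressed and 1 for depressed women.

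- Stated expectation: I0 - I1 > 0 and C0 - C1 > 0.
- Effect modification: (I1 - C1) - (I0 - C0) = (C0 - C1) - (I0 - I1), that is, control-arm gap minus e-SBI-arm gap.

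Two positive numbers can differ in either direction or not at all. The one restriction is that if I0 - I1 > 0, the interaction must be less than C0 - C1.

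**Illustration** (assumed means, SD units):

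| Case | C0 / C1 | I0 / I1 | Control gap | e-SBI gap | Effect, non-depressed | Effect, depressed | Interaction | Expectation met? |
|---|---|---|---|---|---|---|---|---|
| A | 0.5 / 0.2 | 0.8 / 0.5 | 0.3 | 0.3 | 0.3 | 0.3 | 0 | yes |
| B | 0.5 / 0.2 | 0.8 / 0.3 | 0.3 | 0.5 | 0.3 | 0.1 | -0.2 | yes |
| C | 0.5 / 0.0 | 0.8 / 0.5 | 0.5 | 0.3 | 0.3 | 0.5 | +0.2 | yes |
| D | 0.5 / 0.2 | 0.8 / 0.8 | 0.3 | 0 | 0.3 | 0.6 | +0.3 | no |

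Cases A to C all satisfy the expectation with different answers to Aim 4. Case D marks the limit: with a control-arm gap of 0.3, the expectation is compatible with any interaction below +0.3.

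**Comparing two within-arm tests does not repair this.** Take equal true gaps of 0.5 SD in both arms (no modification), 100 per arm and two-sided 5% tests. The SE of a within-arm gap is sqrt(1/(np) + 1/(n(1-p))), where p is the proportion depressed.

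- p = 0.2: SE 0.25, power per arm 0.516. The chance that exactly one arm is significant is 2 × 0.516 × 0.484 = 0.50.
- p = 0.5: SE 0.20, power per arm 0.705. The chance is 2 × 0.705 × 0.295 = 0.42.

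**Precision of the contrast that does answer Aim 4.** SE = sqrt(2 × (1/(np) + 1/(n(1-p)))), outcome SD 1. The half-width is 1.96 × SE. The interaction detectable with 80% power is 2.80 × SE.

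| n per arm | p | SE | 95% half-width | Detectable |
|---|---|---|---|---|
| 100 | 0.2 | 0.354 | 0.69 | 0.99 |
| 100 | 0.3 | 0.309 | 0.60 | 0.86 |
| 100 | 0.4 | 0.289 | 0.57 | 0.81 |
| 80 | 0.2 | 0.395 | 0.77 | 1.11 |
| 80 | 0.3 | 0.345 | 0.68 | 0.97 |
| 80 | 0.4 | 0.323 | 0.63 | 0.90 |

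The 100 per arm comes from Aim 2. The 80 per arm assumes 20% loss. For comparison, the SE of the main arm effect at 100 per arm is sqrt(2/100) = 0.141, so the interaction SE is 2.0 to 2.5 times as large.

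**The case against.** The strongest defence is that the protocol fixes no analysis for Aim 4. The aim is to explore, and the following sentence records an expectation. It is not labelled a test or a criterion for answering the aim. An investigator may explore modification and also say what pattern is likely in each arm. The sentence sits in a short lay summary on an ethics form, and an interaction term with its confidence interval is ordinary SAP content, so its absence here is no fault.

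Much of this is fair. The absence of an interaction model is not the point, and an SAP may contain one. The two gaps also yield the right contrast if one is subtracted from the other. What remains is that the document does state a contrast for Aim 4, and it is the wrong one for the question asked a few lines earlier. An SAP that followed the sentence faithfully would examine prognosis.

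Two further limits are accepted. The bound on the interaction is given on the mean-difference scale, and the protocol names no scale. All SD-unit figures are assumptions that show the logic and the precision; they do not measure harm in this trial.

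**Conclusion.** The concern holds, as a minor one. The Aim 4 expectation addresses whether depression predicts change in drinking, while the aim is whether depression changes the e-SBI effect. Confirming the first leaves the second open, apart from excluding an interaction in favour of depressed women at least as large as the control-arm gap. This follows from the algebra and does not depend on the assumed means, prevalence or attrition. The consequence is confined to an exploratory aim; recruitment, allocation and the main efficacy comparison are unaffected.

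**What to change.** Reword the Aim 4 expectation as a difference in the e-SBI-minus-control effect on drinking between women with and without depression. The investigators should choose the direction, if they expect one. Estimate it as the arm-by-depression interaction with a 95% CI, and report the e-SBI effect in each depression stratum. Keep the within-arm gaps as a description of prognosis only.

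As a precaution, use depression status recorded before allocation if it is collected then. The protocol does not say when depression is measured, so this is not a shown defect.

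The cost is one protocol sentence and one model term, with no extra data. The drawback is low precision: with 80% power only an interaction of about 0.8 to 1.0 SD would be detected with 100 per arm, or about 0.9 to 1.1 SD after 20% loss (20-40% depressed, assumed). The result will probably be inconclusive and should be reported as such.

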Data collection will be conducted at two sites of the Women, Infants and Children (WIC) program that are interested in participating in the proposed study, the Sonoma County WIC site in Santa Rosa, and the La Clinica de la Raza Fruitvale WIC (see letters of interest and organizational support). Data collection with human subjects involves the following: 1) Individual testing of e-SBI and assessment software by a total sample of 20 women at the clinic prior to software finalization to enhance its acceptability and usability for study participants; 2) recruitment of non-pregnant women attending the WIC clinic to participate in a short computerized screening, including that for alcohol use to identify study eligibility. Those reporting drinking 5 or more drinks in a day or 8 or more drinks in a week within the past year will be eligible for the trial. 3) computerized random assignment of c women eligible for the trial to one of two study conditions, i.e., to receive the e-SBI (experimental group) versus usual care (control group); 4) completion of a baseline assessment on alcohol use, any drug and *tobacco* use, sweetened beverage consumption, with the e-SBI for the experimental/intervention group only; 5) completion of 3-month follow-up computerized assessments; and 6) completion of 6-month follow-up computerized assessments.

Study procedures include several tasks as detailed next. Also see Figures 1 and 2 attached that provide an overview of expected recruitment numbers and study procedures.

Adaptation the e-SBI for use with non-pregnant women. Our first study aim is to adapt a recently piloted computerized SBI for drinking during pregnancy for use with non-pregnant women of childbearing age. The adapted e-SBI, like that for drinking during pregnancy, piloted at the Richmond WIC site in 2012-2013, will be self-administered via a computer with a touch-screen monitor. Adaptations include text changes to content to increase relevance of messages for reduced drinking relevant for non-pregnant women who potentially could become pregnant and drink prior to pregnancy recognition. Expert review (consultant, clinic staff) and feedback from women testing our study program in the preparatory period will be used finalize content modifications.

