Development of the computerized study program. Most of the study procedures will be computerized. The computerized study program will include informed consent and all study assessments. It will also deliver the e-SBI to participants who screen eligible and are randomized into the intervention condition, and provide all needed referral information. Thus, the computerized study program will include a) the informed consent b) all study assessments including at baseline, 3 months and 6 months; c) a screening module to identify risky drinkers for study inclusion (those who drink 8 or more drinks in a week or five or more drinks in a day); d) computerized randomization of eligible participants to the two study trial conditions (intervention or the brief alcohol intervention **vs** control or usual care); e) at baseline: a brief alcohol intervention for the intervention group only; f) at the 3-month follow up: a booster (re-administration of) e-SBI for the intervention group; and g) at 3- and 6-month follow up: drink size assessment for both study groups. See study program flowcharts in the attachments for an overview of the modules of the computerized study program.

The Brief Alcohol intervention Like other SBIs, our e-SBI for drinking during pregnancy includes alcohol assessment and feedback, information on alcohol-related harms and benefits of reducing consumption, and a personalized plan for reducing consumption. The plan includes goal setting, an analysis of high risk situations for drinking, and suggested coping strategies. Two components of our e-SBI set it apart from prior interventions: 1) A drink-size assessment that uses *a display of actual drinking vessels (9 glasses) placed above the study computer (see the storyboards for the computerized study program for a picture of the vessels display)*; and photographs or other drink containers (glasses, bottles, cans) to assess beverage-specific drink sizes; 2) Drink size feedback that educates users about standard drink sizes and reviews discrepancies between their drink size and the standard

size for each beverage, highlighting that she may be drinking more than she thinks she does.

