Preparatory Period: This will include testing of study procedures and computerized study program. Following beta testing and elimination of programming errors for the computerized study program, we will use a 2-month preparatory period to test and finalize our computerized study program and the recruitment and data collection procedures at both study sites. This is critical to identify any unanticipated problems and to ensure the study procedures do not impact staff work load.

We will recruit 10 non-pregnant women (5 English speaking and 5 Spanish speaking) at each of the two WIC sites to test the computerized study program. In our prior work with e-SBI for drinking during pregnancy at a Contra Costa county WIC site, we found individual testing of the e-SBI feasible and relevant and used it successfully.

Clinic staff will inform eligible participants about testing of the computerized study program, clarify that participation is voluntary and does not affect services received at the site in any way. Interested participants will approach the private study area where the research assistant will help them review and complete the informed consent. Participants will be paid \$20.00 each for testing the program. No identifying information will be collected from these participants. However, we will ask participants for their WIC ID number to ensure that they do not participate again in the study.

Recruitment of participants for the study

Posters and recruitment flyers leaflets that provide basic information about the study as a health study will be used for recruitment (see attachment). Posters, with the same information as the flyers but in larger size, will be placed in visible areas identified in close consultation with staff at each site. WIC staff will inform eligible women about the study by providing them a copy of the recruitment flyer with brief study information at the end of their visit and will indicate where the private study area is located. WIC staff will clarify to clients that study participation is voluntary, they will not know who participated or not as no study data is shared with staff, and that study participation will not affect clients WIC services in any way. Interested women will then approach the Research Assistant (RA) on site.

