Study consent will be administered electronically. In reviews for our prior e-SBI study with pregnant women, electronic consent (by selecting "I agree" on the pertinent screen) was deemed acceptable for research purposes by both the Public Health Institute and the Contra Costa County Regional Medical Center Institutional Review Boards. A participant may decline or stop participation at any point during the study by pressing a stop sign present on each screen of the computerized study program. If the participant presses "stop", the computer will ask if it may store the data allowing the participant to select a response to eliminate the data. Because data on

where women stop the program is useful for program improvements, we will delete that participants data at the end of the day after recording which program screen she touched the stop button on. Women completing screening who report risky drinking will be eligible for the trial. The computer will randomly assign these women to receive the alcohol intervention or not and then to complete the baseline assessment

Women will use the computerized program independently, with the RA available on site to answer questions and address any unanticipated problems. At completion of the program, an encrypted email will be generated to the RA which includes the following password-protected information, none of which is personal identifying information: Study-ID and whether screening only vs full baseline assessment was completed. The program will also prompt participants to meet the RA to collect their payment and provide needed follow up information. The RA will a) provide the incentive payment (gift card); and b) obtain contact information for purposes of follow-up. Participants will be paid \$5.00 if screened only and \$30.00 each for baseline and follow-up assessments if enrolled in the trial. Contact information obtained will include the participants' name, phone number and other contact information needed to reach them to schedule their follow up appointments. All follow-up appointments will be scheduled to coincide with subsequent visits to the WIC site. The RA will explain to participants that all identifying information collected will be confidential, secured and kept separate from the data.

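### Women are randomised before the full baseline assessment, and one sentence read literally also puts the e-SBI before it, so baseline drinking may be contaminated in one arm

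*Protocol*

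**What the plan says.** The order of events at the first visit is described in three places in Protocol section 2(a).

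- **Consent and randomisation paragraph.** After screening, "The computer will randomly assign these women to receive the alcohol intervention or not and then to complete the baseline assessment". Of the text shown, this is the only sentence that puts the e-SBI and the baseline assessment in sequence.
- **Numbered list of procedures.** Random assignment is step 3. The baseline assessment, which covers alcohol use, is step 4, "with the e-SBI for the experimental/intervention group only". The order within step 4 is not given.
- **Development of the computerized study program.** Item e reads "at baseline: a brief alcohol intervention for the intervention group only", without saying whether this comes before or after the questions. Item g lists "at 3- and 6-month follow up: drink size assessment for both study groups", so controls first meet that component at 3 months.

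The e-SBI gives feedback on drink size, "highlighting that she may be drinking more than she thinks she does". Screening precedes allocation and determines eligibility: "Those reporting drinking 5 or more drinks in a day or 8 or more drinks in a week within the past year". Aim 4 (section 1(a)) expects that "within the intervention and control group each, women reporting depression will reduce their drinking less than those without depression". Section 2(a) refers to Figures 1 and 2, program flowcharts and storyboards; none is available here.

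**The concern.** A baseline value serves as a reference for change, or as a covariate, only if treatment cannot have affected it. If the e-SBI runs first, one arm answers the baseline drinking questions after being taught about standard drinks and told that its own count may be too low, while the other arm answers without that information. Past drinking cannot change within a session, but its reporting can.

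The direction is unknown. Feedback that raises reported baseline drinking would exaggerate the benefit of the e-SBI; feedback that lowers it would hide benefit. Aim 4 is worded as a reduction in drinking, which reads as change from baseline, so the protocol does rely on this measurement. The drinking data certain to precede allocation are the screening items, described as past-year thresholds that every randomised woman meets. They might serve as a covariate, but on that description not as the reference for change at 3 or 6 months.

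Allocation before baseline is a separate and smaller matter. It does not by itself bias a comparison of follow-up values, but women who stop between allocation and the end of baseline become losses after randomisation.

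**Working it through.** **Order of events.** The quoted sentence and the numbered list agree that allocation precedes baseline. For the e-SBI, the sentence read literally gives assign, e-SBI or nothing, then baseline. The numbered list and item e fit either order. This is therefore an ambiguity rather than a contradiction, but no text shown says that baseline is finished before allocation or before feedback.

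**Inputs.** 100 women per arm (Aim 2). The protocol gives no effect size, SD, alpha or power, so there is no stated figure to reproduce. Everything else is assumed: outcome SD 1, true effect 0, two-sided 5% test, baseline-outcome correlation rho of 0.5 or 0.7, and a shift of d SD in reported baseline in the e-SBI arm only.

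**Bias if the e-SBI comes first.** Change score: d. Baseline-adjusted: rho × d. Follow-up values alone: 0.

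**Standard errors (N = 200).**
- Change: sqrt(2(1 − rho) × 4/200) = 0.141 (rho 0.5) or 0.110 (rho 0.7).
- Adjusted: sqrt((1 − rho²) × 4/200) = 0.122 or 0.101.
- Follow-up only: sqrt(4/200) = 0.141.

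**False rejection**, from the normal distribution with mean bias/SE and critical value 1.96:

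| Shift d (SD) | Change bias | Change, rho 0.5 / 0.7 | Adjusted bias, rho 0.5 / 0.7 | Adjusted, rho 0.5 / 0.7 |
|---|---|---|---|---|
| 0.1 | 0.10 | 10.9% / 15.0% | 0.05 / 0.07 | 6.9% / 10.7% |
| 0.2 | 0.20 | 29.3% / 44.7% | 0.10 / 0.14 | 12.9% / 28.3% |
| 0.3 | 0.30 | 56.4% / 78.2% | 0.15 / 0.21 | 23.2% / 54.8% |

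A simulation at d = 0.2 (8,000 replicates, t-test and ANCOVA) gave 29.1% / 44.5% for change, 12.8% / 27.8% adjusted, and 5.3% / 5.3% for follow-up only.

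**Price of dropping baseline.** The effect detectable with 80% power is 2.802 × SE: 0.40 SD from follow-up values alone, against 0.34 SD (rho 0.5) or 0.28 SD (rho 0.7) with a valid covariate. Since 200 × (1 − rho²) = 150 or 102, an analysis of 200 women on follow-up values alone is only as precise as 150 or 102 women with a sound baseline covariate.

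**Allocation order alone (e-SBI after baseline).** Simulated loss between allocation and the end of baseline (8,000 replicates; severity-outcome correlation 0.6; log-odds of loss rising 0.7 per SD of severity; unadjusted comparison of women not lost):

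| Loss, control / e-SBI | Loss depends on severity in | Bias (SD) | Rejection |
|---|---|---|---|
| 5% / 5% | both arms | −0.001 | 5.2% |
| 10% / 10% | both arms | 0.000 | 5.2% |
| 5% / 10% | both arms | −0.019 | 5.5% |
| 5% / 10% | e-SBI only | −0.037 | 5.7% |

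**Aim 4.** A reporting shift equal in women with and without depression cancels in the within-arm comparison; one that differs between them does not.

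**The case against.** The strongest reply is that the literal reading is not the intended one. The protocol often uses the word assessment for the whole computer session. Section 5(g) budgets three assessments of at most 25-30 minutes, 1.5 hours in all, with no separate allowance for the e-SBI. Section 6(d) describes controls as receiving assessment without the intervention, which suits a shared assessment followed by an addition in one arm. Section 1(a) has the tool collect drink sizes before giving feedback on them, so some drinking data must precede feedback in the e-SBI arm. The attachments may fix the order outright.

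This makes the looser reading plausible, and it is why the point is called an ambiguity. It does not settle where the baseline questions fall, and the sentence describes software behaviour that could be programmed as written. If the attachments put baseline first, the sentence still misdescribes the order and needs correcting.

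Three further points stand in part. The shifts of 0.1 to 0.3 SD have no anchor in the protocol, and no between-arm change-score or baseline-adjusted analysis is named there, so the rejection rates only illustrate scale. The screening items themselves are not shown and may record more than thresholds. And the one part that is certain, allocation before baseline, does little harm by itself.

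**Conclusion.** The concern holds and should be fixed, with medium confidence because the attachments could resolve the main part. Allocation precedes the full baseline assessment in both places that order them, and the only sentence that orders the e-SBI against baseline puts the e-SBI first if read as written.

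If it is run that way, a one-arm reporting shift of 0.1 to 0.3 SD would bias change scores by the same amount and adjusted effects by 0.05 to 0.21 SD, with false rejection of 11-78% and 7-55% respectively. Without a shift there is no bias, and neither the size nor the direction of a shift can be told from the protocol. Comparing follow-up values alone avoids the bias but gives up precision. If the e-SBI already follows baseline, what remains is small: 0.00-0.04 SD and 5-6% rejection under the loss patterns simulated. The order of data collection has to be right before the first woman is enrolled; analysis cannot repair it later.

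**What to change.** State one order and use it throughout: consent, screening, full baseline assessment, computer randomisation, then e-SBI or exit. Keep the drink-size assessment inside the e-SBI, so that controls still first meet it at 3 months. Amend the three descriptions in section 2(a), and the figures, flowcharts and storyboards where they differ. Leave the data-deletion rules in sections 2(a), 5(e) and 6(a) as they are, and count stops after allocation by arm among women who allow their data to be stored. The program must hold the arm anyway, for the 3-month booster and the pregnancy reminder.

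If the attachments already place baseline before the e-SBI, correcting the one sentence removes the main concern; moving randomisation then removes only the small one.

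The timing is favourable: "we will use a 2-month preparatory period to test and finalize our computerized study program". The cost is moving one step in that software, revising attachments where needed, and an amendment reviewed by the IRBs, since the document is already approved. Women in the e-SBI arm would reach the intervention later in a session of at most 25-30 minutes. No questions are added.
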